**Table 5.1-5: Follow-Up Period (CA209672) –Part 1, Arm A and C**

Procedure	Follow-Up Visit 1 a Last Visit + 30 days ( $\pm 7$ days)	Follow-Up Visit 2 Previous Follow-up Visit + 70 Days ( $\pm 7$ days)	Notes
Safety Assessments			
Targeted Physical Examination, Measurements, Vital Signs, Oxygen Saturation and Performance Status	x	x	To assess for potential late emergent study drug related issues. Weight, BP, HR, temperature, oxygen saturation and ECOG status. Targeted physical examination to be performed only as clinically indicated.
Adverse Events Assessment (Including SAE)	x	x	All AEs to be collected for 100 days after last dose of nivolumab treatment. Participants will be followed for all SAEs, non-serious AEs of special interest, and all AEs associated with confirmed or suspected SARS-CoV-2 infection until resolution, the condition stabilizes, the event is otherwise explained, the event is deemed irreversible, the participant is lost to follow-up, or for suspected cases, until SARS-CoV-2 infections is ruled out.
Review of Concomitant Medications	x	x	
ECG		x	As clinically indicated or for study drug related toxicities.
Laboratory Tests		See Notes	On site/local laboratory testing. To be performed at FU1. To be repeated at FU2 if study drug related toxicity persists.  CBC w/differential; Full Chemistry Panel: LDH, AST, ALT, ALP, T.Bili, (Direct Bili if T.Bili > ULN), BUN (or serum urea level), creatinine, Ca+, Mg+, Na+, K+, Cl-, glucose, albumin, T.Protein
Thyroid function		See Notes	On site/local laboratory testing. To be performed at FU1. To be repeated at FU2 if study drug related toxicity persists. TSH, (free T3, Free T4 if TSH not within normal limits)

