**Table 5.1-5: Follow-Up Period (CA209672) –Part 1, Arm A and C**

Procedure	Follow-Up Visit 1 a Last Visit + 30 days ( $\pm 7$ days)	Follow-Up Visit 2 Previous Follow-up Visit + 70 Days ( $\pm 7$ days)	Notes
Pregnancy Test	x	x	Serum or urine
Pharmacokinetic (PK) Assessmentsb			
Blood PK Sampling	Refer to Table 5.5.1-2 for specific PK sampling time points.		
Immunogenicity (ADA) Assessmentsb			
Blood ADA Sample	Refer to Table 5.5.1-1 for specific ADA sampling time points. See Section 5.5 .		

a When a participant discontinues study drug treatment, all remaining visits of that treatment cycle should be completed (without infusion and with only a single pharmacokinetic sample taken at applicable visits), and the participant should enter the Follow-up Period (Follow-up 1 and then Follow-up 2). When a participant is withdrawn from the study (during the Treatment or Follow-up Period), all evaluations associated with that study visit should be performed and the date and reason for study discontinuation should be documented on the CRF. Follow-up visit #1 (FU1) occurs approximately 30 days after the last dose ( $\pm 7$  days) or coincides with the date of discontinuation ( $\pm 7$  days) if date of discontinuation is greater than 30 days after last dose. Follow-Up Visit #2 (FU2) occurs approximately 70 days ( $\pm 7$  days) after FU1. Both Follow Up visits should be conducted in person.

b As of Protocol Amendment 07: Assessments necessary for monitoring safety will continue per protocol until FU2 or 100 days after study drug discontinuation, whichever occurs later. Collection of PK and immunogenicity data is not applicable. Analyses of PK and immunogenicity will be based on the samples analyzed before implementation of protocol amendment 07.

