with the date of discontinuation ( $\pm$  7 days) if date of discontinuation is greater than 35 days after last dose. Follow-Up Visit #2 (FU2) occurs approximately 70 days ( $\pm$  7 days) after FU1. Both Follow Up visits should be conducted in person.

b As of Protocol Amendment 07: Assessments necessary for monitoring safety and tumor assessments will continue per protocol until FU2 or 100 days after study drug discontinuation, whichever occurs later.

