## **8.3 Endpoints**

### **8.3.1 Primary Endpoint(s)**

#### **8.3.1.1 Part 1**

The primary objective of Part 1 is to characterize the safety and tolerability of nivolumab plus ipilimumab in Chinese participants. The primary objective will be measured by:

- Number and percent of all treated participants that experience AEs occurring up to 100 days after the last dose of study drug (time frame - on a continuous basis up to 100 days after the last dose of study drug)
- Number and percent of all treated participants that experience SAEs occurring up to 100 days after the last dose of study drug (time frame - on a continuous basis up to 100 days after the last dose of study drug)
- Number and percent of all treated participants that experience AEs leading to discontinuation occurring up to 100 days after the last dose of study drug (time frame - on a continuous basis up to 100 days after the last dose of study drug)

- Number and percent of all treated participants that experience AEs leading to death occurring up to 100 days after the last dose of study drug (time frame - on a continuous basis up to 100 days after the last dose of study drug)
- Number and percent of participants with clinical laboratory abnormalities by worst toxicity grade by NCI CTCAE version 4.0 (as assessed at the planned times listed in [Table 5.1-1](#), [Table 5.1-2](#), [Table 5.1-3](#), [Table 5.1-4](#), [Table 5.1-5](#), [Table 5.1-6](#) and [Table 5.1-7](#)) (time frame - on a continuous basis up to 100 days after the last dose of study drug)

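### The Part 1 primary laboratory measure is labelled as running to 100 days after last dose, but the last unconditional test is at FU1, and the timing of FU1 is stated in conflicting ways

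*Combined protocol and SAP*

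**What the plan says.** Section 8.3.1.1 lists five Part 1 primary safety measures: adverse events, serious adverse events, events leading to discontinuation, events leading to death, and laboratory abnormalities by worst grade. All five carry the same label: "time frame - on a continuous basis up to 100 days after the last dose of study drug". The laboratory measure is also defined by reference to the assessment times in the schedule tables. The Synopsis lists it with that reference but without a 100-day time frame.

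The follow-up tables (5.1-5 for Arms A and C, 5.1-6 for Arm B, 5.1-7 for Arm D) contain two visits:

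- The header places FU1 at "Last Visit + 30 days ( $\pm 7$ days").
- Footnote a of Table 5.1-5 says instead that "Follow-up visit #1 (FU1) occurs approximately 30 days after the last dose", with the same 7-day tolerance, or on the date of discontinuation "if date of discontinuation is greater than 30 days after last dose". Table 5.1-6 repeats this. Table 5.1-7 has a different threshold: "if date of discontinuation is greater than 35 days after last dose".
- The same footnote says that after drug is stopped "all remaining visits of that treatment cycle should be completed", so the last visit can be later than the last dose.
- FU2 is headed "Follow-Up Visit 2 Previous Follow-up Visit + 70 Days", again with a 7-day tolerance.
- Laboratory and thyroid tests are "To be performed at FU1. To be repeated at FU2 if study drug related toxicity persists".

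Adverse event collection is stated separately. The adverse event row of each table and Section 3.1.5 require all events for 100 days after last dose. Section 6.2.1 sets a minimum of 100 days after discontinuation. Footnote b continues safety assessments to the later of FU2 and 100 days after discontinuation.

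**The concern.** A worst-grade table labelled as covering 100 days implies that every participant could have shown an abnormality throughout that period. Here, after FU1, a scheduled test depends on earlier toxicity. A participant with clean FU1 results who then develops a new abnormality does not meet the condition for the FU2 test. Late worst grades are therefore looked for mainly in participants already known to have toxicity, which is outcome-dependent ascertainment in a primary measure.

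The conflicting FU1 anchors make this worse, because two sites can follow the protocol and place FU1, and with it FU2, weeks apart relative to the last dose. Each Part 1 arm has 9 participants, so one participant whose true worst grade is missed changes an arm's percentage by 1/9, or 11 percentage points.

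**Working it through.** Inputs: FU1 at 30 ± 7 days and FU2 at FU1 + 70 ± 7 days (headers and footnote a); the 100-day window (Section 8.3.1.1); a 6-week cycle with a Day 42 visit (Tables 5.1-2 and 5.1-3). Days below count from the last dose unless stated.

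1. **Nominal schedule.** 30 + 70 = 100, which reproduces the plan's 100 days.

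2. **Last-dose anchor.** FU1: 30 − 7 = 23 to 30 + 7 = 37. FU2: earliest 23 + 63 = 86, latest 37 + 77 = 114. An earliest FU2 is 100 − 86 = 14 days short.

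3. **Discontinuation anchor.** Discontinuation on Day 31, the first day this applies in Tables 5.1-5 and 5.1-6, gives FU1 on Day 24 to 38 and FU2 on Day 87 to 115. In Table 5.1-7 the first such day is Day 36, giving FU1 on Day 29 to 43 and FU2 on Day 92 to 120. Later discontinuation moves both visits further out, so Day 37 is not a general upper limit for FU1.

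4. **Last-visit anchor (header).** If the last visit is the last dose, the result is as in step 2. If the last dose is on Day 1 of a cycle and the Day 42 visit is completed, the last visit is 42 − 1 = 41 days after the dose. Nominal FU1 is then 41 + 30 = 71, against 30 under the footnote when discontinuation is within 30 days. The difference is 41 days. The footnote's FU1 (cycle Day 24 to 38) also comes before the Day 42 visit that the same footnote requires to be completed before follow-up starts. The header's FU2 is 41 + 86 = 127 to 41 + 114 = 155.

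5. **When an early FU2 is possible under the header.** The earliest FU2 is 86 plus the gap between last dose and last visit. With a gap of 14 days or more it is never before Day 100 (14 + 86 = 100). The early FU2 and the 41-day discrepancy are therefore not cumulative.

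6. **Laboratory coverage without persisting toxicity.** On the last-dose anchor, the time from FU1 to Day 100 is 100 − 37 = 63 to 100 − 23 = 77 days. In the extreme header case of step 4, FU1 is on Day 64 to 78, leaving 100 − 78 = 22 to 100 − 64 = 36 days. A stretch without a scheduled test remains in both cases.

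7. **Adverse event coverage.** The collection rules run to 100 days independently of the FU2 date. An early FU2 leaves up to 14 days in which the rule applies but the tables list no further contact.

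**The case against.** The strongest reply is that the laboratory measure is defined by the planned assessment times, and that FU1 plus a conditional FU2 test are those times. Section 5.3 also allows extra tests when clinically indicated, and Section 6.3 sends clinically significant results to the adverse event page. This has force: the analysis can be carried out as defined, and symptomatic late events have a route into the data. It does not rescue the label. The same bullet also states a continuous 100-day time frame, and indicated testing does not find silent abnormalities in a participant with clean FU1 results.

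A reader might infer that the whole 100-day primary safety window is uncovered after an early FU2. The documents do not support that. Adverse events, serious adverse events, events leading to discontinuation and deaths, four of the five measures, must be collected to 100 days regardless of FU2. The footnote b marker sits only on the pharmacokinetic and immunogenicity rows in Table 5.1-5, but its text covers safety, and Table 5.1-6 attaches it to the safety heading.

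A reader might also extend the point to a primary endpoint in Arm D. Safety there is exploratory (Section 8.3.3.2), and footnote a of Table 5.1-7 is not the same as in the Part 1 tables.

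Nor do the documents call for amylase and lipase in follow-up, since Section 6.3.1 designates them as on-treatment tests. A compulsory FU2 draw for everyone would run against the burden reduction that Amendment 07 sets out to achieve.

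**Conclusion.** The point stands for the Part 1 laboratory measure. Its 100-day label is not delivered by the schedule: 63 to 77 days have no scheduled test on the last-dose anchor unless toxicity persists, and fewer if FU1 is later. The FU1 anchor is contradictory by up to 41 days in the Day 1 / Day 42 case, and the discontinuation threshold differs between tables (30 versus 35 days).

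For the other four primary measures the residual defect is small: no contact is scheduled for up to 14 days after an early FU2. This does not show that events are missed. The share of FU2 visits falling before Day 100 depends on how sites book within the windows, which the documents do not report, so no share is given. The ranges assume that visits stay within their stated tolerances; the 41-day figure also assumes discontinuation within 30 days of last dose and a Day 42 visit on its nominal day.

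**What to change.** 1. In Tables 5.1-5 to 5.1-7, reconcile the headers and footnote a to one FU1 anchor, consistent with the last-dose clock of the endpoints in Section 8.3.1.1, and state how FU1 relates to the remaining cycle visits. Reconcile the 30- and 35-day discontinuation thresholds. Cost: text only.

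2. Set the FU2 window so that the last adverse event contact does not precede Day 100 after last dose, or state that a phone contact at Day 100 completes collection when FU2 is earlier. Cost: some contacts up to two weeks later, or one added call. If FU2 itself is moved, check it against the 100-day follow-up limit in Section 3.1.1 and the limits on Arm D collection in Table 5.1-7; the phone contact avoids that conflict.

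3. In Section 8.3.1.1, restate the laboratory time frame as through FU1, and report FU2 laboratory results separately as toxicity-triggered. Do not label the worst-grade table as covering 100 days. Cost: wording and one additional display, with no new procedure. This also works for participants who have already completed follow-up.

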**Table 5.1-5: Follow-Up Period (CA209672) –Part 1, Arm A and C**

Procedure	Follow-Up Visit 1 a Last Visit + 30 days ( $\pm 7$ days)	Follow-Up Visit 2 Previous Follow-up Visit + 70 Days ( $\pm 7$ days)	Notes
Pregnancy Test	x	x	Serum or urine
Pharmacokinetic (PK) Assessmentsb			
Blood PK Sampling	Refer to Table 5.5.1-2 for specific PK sampling time points.		
Immunogenicity (ADA) Assessmentsb			
Blood ADA Sample	Refer to Table 5.5.1-1 for specific ADA sampling time points. See Section 5.5 .		

a When a participant discontinues study drug treatment, all remaining visits of that treatment cycle should be completed (without infusion and with only a single pharmacokinetic sample taken at applicable visits), and the participant should enter the Follow-up Period (Follow-up 1 and then Follow-up 2). When a participant is withdrawn from the study (during the Treatment or Follow-up Period), all evaluations associated with that study visit should be performed and the date and reason for study discontinuation should be documented on the CRF. Follow-up visit #1 (FU1) occurs approximately 30 days after the last dose ( $\pm 7$  days) or coincides with the date of discontinuation ( $\pm 7$  days) if date of discontinuation is greater than 30 days after last dose. Follow-Up Visit #2 (FU2) occurs approximately 70 days ( $\pm 7$  days) after FU1. Both Follow Up visits should be conducted in person.

b As of Protocol Amendment 07: Assessments necessary for monitoring safety will continue per protocol until FU2 or 100 days after study drug discontinuation, whichever occurs later. Collection of PK and immunogenicity data is not applicable. Analyses of PK and immunogenicity will be based on the samples analyzed before implementation of protocol amendment 07.

**Table 5.1-6: Follow-Up Period (CA209672) –Part 1, Arm B**

Procedure	Follow-Up Visit 1 a Last Visit + 30 days ( $\pm 7$ days)	Follow-Up Visit 2 Previous Follow-up Visit + 70 Days ( $\pm 7$ days)	Notes
Safety Assessmentsb			
Targeted Physical Examination, Measurements, Vital Signs, Oxygen Saturation and Performance Status	x	x	To assess for potential late emergent study drug related issues. Weight, BP, HR, temperature, oxygen saturation and ECOG status. Targeted physical examination to be performed only as clinically indicated.
Adverse Events Assessment (Including SAE)	x	x	All AEs to be collected for 100 days after last dose of nivolumab treatment.
Review of Concomitant Medications	x	x	
ECG		x	As clinically indicated or for study drug related toxicities.
Laboratory Tests		See Notes	On site/local laboratory testing. To be performed at FU1. To be repeated at FU2 if study drug related toxicity persists. CBC w/differential; Full Chemistry Panel: LDH, AST, ALT, ALP, T.Bili, (Direct Bili if T.Bili > ULN), BUN (or serum urea level), creatinine, Ca+, Mg+, Na+, K+, Cl-, glucose, albumin, T.Protein
Thyroid function		See Notes	On site/local laboratory testing. To be performed at FU1. To be repeated at FU2 if study drug related toxicity persists. TSH, (free T3, Free T4 if TSH not within normal limits)
Pregnancy Test	x	x	Serum or urine

**Table 5.1-6: Follow-Up Period (CA209672) –Part 1, Arm B**

Procedure	Follow-Up Visit 1 a Last Visit + 30 days ( $\pm 7$ days)	Follow-Up Visit 2 Previous Follow-up Visit + 70 Days ( $\pm 7$ days)	Notes
Participant Status			
Survival Status and Subsequent Therapy Information	x	x	May be accomplished by visit, phone contact, or email.
Pharmacokinetic (PK) Assessmentsb			
Blood PK Sampling	Refer to Table 5.5.1-2 for specific PK sampling time points.		
Immunogenicity (ADA) Assessmentsb			
Blood ADA Sample	Refer to Table 5.5.1-1 for specific ADA sampling time points. See Section 5.5 .		

a When a participant discontinues study drug treatment, all remaining visits of that treatment cycle should be completed (without infusion and with only a single pharmacokinetic sample taken at applicable visits), and the participant should enter the Follow-up Period (Follow-up 1 and then Follow-up 2). When a participant is withdrawn from the study (during the Treatment or Follow-up Period), all evaluations associated with that study visit should be performed and the date and reason for study discontinuation should be documented on the CRF. Follow-up visit #1 (FU1) occurs approximately 30 days after the last dose ( $\pm 7$  days) or coincides with the date of discontinuation ( $\pm 7$  days) if date of discontinuation is greater than 30 days after last dose. Follow-Up Visit #2 (FU2) occurs approximately 70 days ( $\pm 7$  days) after FU1. Both Follow Up visits should be conducted in person.

b As of Protocol Amendment 07: Assessments necessary for monitoring safety will continue per protocol until FU2 or 100 days after study drug discontinuation, whichever occurs later. Collection of PK and immunogenicity data is not applicable. Analyses of PK and immunogenicity will be based on the samples analyzed before implementation of protocol amendment 07.

**Table 5.1-7: Follow-Up Period (CA209672) –Part 2, Arm D**

Procedure	Follow-Up Visit 1 a Last Visit + 30 days ( $\pm 7$ days)	Follow-Up Visit 2 Previous Follow-up Visit + 70 Days ( $\pm 7$ days)	Notes
Safety Assessmentsb			
Targeted Physical Examination, Measurements, Vital Signs, and Performance Status	x	x	To assess for potential late emergent study drug related issues. Weight, BP, HR, temperature, and ECOG status. Targeted physical examination to be performed only as clinically indicated.
Adverse Events Assessment (Including SAE)	x	x	All AEs to be collected for 100 days after last dose of nivolumab treatment. For participants assigned to treatment and never treated with study drug, SAEs should be collected for 30 days from the date of treatment assignment.
Review of Concomitant Medications	x	x	
ECG	x		As clinically indicated or for study drug related toxicities.
Laboratory Tests	See Notes		On site/local laboratory testing. To be performed at FU1. To be repeated at FU2 if study drug related toxicity persists. CBC w/differential; Full Chemistry Panel: LDH, AST, ALT, ALP, T.Bili, (Direct Bili if T.Bili > ULN), BUN (or serum urea level), creatinine, Ca+, Mg+, Na+, K+, Cl-, glucose, albumin, T.Protein
Thyroid function	See Notes		On site/local laboratory testing. To be performed at FU1. To be repeated at FU2 if study drug related toxicity persists. TSH, (free T3, Free T4 if TSH not within normal limits)
Pregnancy Test	x	x	Serum or urine

**Table 5.1-7: Follow-Up Period (CA209672) –Part 2, Arm D**

Procedure	Follow-Up Visit 1 a Last Visit + 30 days ( $\pm 7$ days)	Follow-Up Visit 2 Previous Follow-up Visit + 70 Days ( $\pm 7$ days)	Notes
Efficacy Assessments			
Tumor assessments b		Participants who enter the follow-up period will continue to have tumor imaging assessments by investigators and BICR as per on-treatment schedule: every 6 weeks from date of first dosing for the first 24 weeks, and then every 12 weeks thereafter until initiation of subsequent anti-cancer treatment or until 100 days post study drug discontinuation. See Section 5.4 for details on methodology.	
Brain Imaging		Participants with a history of brain metastasis or symptoms should have surveillance MRI per standard of care (approximately every 12 weeks) or sooner if clinically indicated. See Section 5.4 for further details. No brain imaging beyond 100 days post study drug discontinuation is necessary.	
Other Imaging (eg., Bone Scan)		As clinically indicated per local standards. See Section 5.4 for further details. No other imaging beyond 100 days post study drug discontinuation is necessary.	
Outcomes Research Assessments			
QLQ-C30 Questionnaire	x	x	No collection beyond 100 days post study drug discontinuation is necessary.
EQ-5D-3L Questionnaire	x	x	Can be collected either during a clinic visit or by telephone. No collection beyond 100 days post study drug discontinuation is necessary.
Participant Status			
Survival Status and Subsequent Therapy Information	x	x	May be accomplished by visit, phone contact, or email. No collection beyond 100 days post study drug discontinuation is necessary.

a When a participant discontinues study drug treatment, all remaining visits of that treatment cycle should be completed (without infusion and with only a single pharmacokinetic sample taken at applicable visits), and the participant should enter the Follow-up Period (Follow-up 1 and then Follow-up 2). When a participant is withdrawn from the study (during the Treatment or Follow-up Period), all evaluations associated with that study visit should be performed and the date and reason for study discontinuation should be documented on the CRF. Follow-Up Visit #1 (FU1) occurs approximately 30 days ( $\pm 7$  days) after last dose or coinciding

with the date of discontinuation ( $\pm$  7 days) if date of discontinuation is greater than 35 days after last dose. Follow-Up Visit #2 (FU2) occurs approximately 70 days ( $\pm$  7 days) after FU1. Both Follow Up visits should be conducted in person.

b As of Protocol Amendment 07: Assessments necessary for monitoring safety and tumor assessments will continue per protocol until FU2 or 100 days after study drug discontinuation, whichever occurs later.

### **5.1.1     Retesting During Screening or Lead-in Period**

This study is not actively enrolling participants.

Retesting of laboratory parameters and/or other assessments within any single Screening period will be permitted (in addition to any parameters that require a confirmatory value).

Any new result will override the previous result (ie, the most current result prior to dosing) and is the value by which study inclusion will be assessed, as it represents the participant's most current, clinical state.

Laboratory parameters and/or assessments that are included in [Table 5.1-1](#), Screening Procedural Outline, may be repeated in an effort to find all possible well-qualified participants. Consultation with the medical monitor may be needed to identify whether repeat testing of any particular parameter is clinically relevant.

